5.0 Definitions and Study Assessments

5.1 Definitions

Baseline

Unless stated otherwise, the baseline is defined as the last non-missing assessment prior to the first administration of investigational medicinal product (IMP). If the assessment time is missing while the assessment date is the same date as the first administration of investigation product, a scheduled pre-dose assessment will be considered as baseline.

Change from Baseline

Change from baseline is defined as (value at post-baseline visit – value at baseline). Similarly percentage change from baseline is defined as $100 \times (\text{change from baseline})/\text{baseline}$.

Concomitant and Prior Medication

Prior medications are defined as medications with a start date prior to first dose of IMP. Concomitant medications are defined as any medications ongoing at the start of IMP treatment or with a start date on or after the first IMP dose date. Consequently, medications ongoing at the start of IMP will be reported as both prior and concomitant medications.

Study Day 1

The first day IMP is administered.

Study Day

Study day is defined as the number of days from Study Day 1.

- Before Study Day 1, Study Day = (Date of Interest – Date of Study Day 1)
- On or After Study Day 1, Study Day = (Date of Interest – Date of Study Day 1) + 1

Therefore the day prior to Study Day 1 is Study Day -1.

Study Visit

For by-visit summaries, data will be assigned to visits using windowing (see below). If more than one actual visit (including the early termination or unscheduled visits) falls within the same defined window, the visit closest to the target day with non-missing data will be considered for analysis. If two actual visit dates are at the same distance from the target day, the latest visit with non-missing data will be considered for analysis.

| Study Analysis Visit | Target Day | Study Day | Interval (days) |
|--|--------------------------|----------------------------|-------------------------------|
| Baseline | 1 | ≤1* | NA |
| Day 7 (Cohorts 2 & 3 only) | 7 | 5 to 9 | 5 |
| Week 4 | 28 | 21 to 38 | 18 |
| Week 8 | 56 | 49 to 66 | 18 |
| Week 12 | 84 | 67 to 112 | 46 |
| Week 24 | 168 | 140 to 196 | 57 |
| Week 36 | 252 | 224 to 280 | 57 |
| Week 48 | 336 | 308 to 364 | 57 |
| Week 60 | 420 | 392 to 448 | 57 |
| Week W | W x 7 | (W x 7 -28) to (W x 7 +28) | 57 |
| And so forth for 3 monthly visits | | | |

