5.2 Efficacy Assessments

All of the efficacy endpoints will be assessed at baseline, end of study, and Weeks 12, 24, 36 and 48 during the first 48 weeks and then 6 monthly during the extension phase. If a subject withdraws from the study prematurely they will also be assessed at the termination visit.

The 6MWT will also be conducted at screening.

In the sections below reference is made to reasons for not performing an assessment or not completing an assessment. Different approaches will be taken for dealing with the missing data dependent on whether or not the reason is related to the subject's medical condition (i.e. informative). A reason of 'Subject physically unable' will be regarded as informative, whilst 'Site staff/facility unavailable' is not informative. Other reasons will require a team review on a case-by-case basis.

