5.2.1 Six-Minute Walk Distance

The total distance walked during six-minutes will be recorded in the eCRF. Subjects in both Cohorts 1 and 2 are required to be ambulatory at Baseline. If the subject is unable to perform the assessment after Day 1 or is unable to complete it, the reason will be recorded. For an assessment not completed the duration of time walked will also be recorded.

If the reason given for not performing the assessment or not completing the assessment is related to the subject's medical condition (i.e. informative) the 6MWD will be taken as zero or the recorded 6MWD respectively. However, if the reason is not deemed to be related to their medical condition (i.e. non-informative) then the distance will be taken as missing.

The use of orthoses or aids will also be recorded. The 6MWD recorded will still be used in analyses, but the use of orthoses or aids will be summarized.

The number of falls or times the follower provides support will also be recorded. This will not impact the use of the 6MWD recorded, but will be summarized separately.

The %-predicted 6MWD will be calculated using the equation proposed by [Geiger \(2007\)](#):

Male 6MWD=196.72+ (39.81 x age) – (1.36 x age²) + (132.28 x height), where age is age at assessment (not integer age) in years and height is height at assessment in meters.

Changes from baseline will be calculated for 6MWD and %-predicted 6MWD. Baseline will be the average of the pre-dose measurements.

The following velocities of change (change per month) will also be calculated for both the 6MWD and the %-predicted 6MWD:

- Baseline to Week 12
- Week 12 to Week 24
- Week 24 to Week 36
- Week 36 to Week 48

And

- Baseline to Week 24
- Week 24 to Week 48

... and so forth when reporting the extension phase data

The time till a 10% reduction in 6MWD will be determined for each subject. The occurrence of this reduction will have to be confirmed by the next visit attended.

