The 10-metre run/walk should be performed once at each visit and only repeated if the evaluator deems it to be spurious. The protocol incorrectly states that the test should be repeated after a 10 minute rest and both times recorded on the eCRF. The error was documented in a file note (SMTC11005-006 Dated: 05Oct2017). As a consequence, the majority of patients only have one test performed at a visit however if there is a repeat test then the shortest time (duration) of the completed tests will be used in analyses. If the subject is unable to perform the assessment or is unable to complete it, the reason will be recorded. For an assessment not completed the distance and duration of time walked will also be recorded.

If the reason given for not performing at any assessment or not completing any assessment is related to the subject's medical condition (i.e. informative) the time will be taken as the worst score recorded (over all subjects and assessments) whilst on treatment or the derived time adjusted for the distance recorded respectively.

The derived time adjusted for the distance = (10/distance in metres) x time recorded.

Changes from baseline will be calculated.

The following velocities of change (change per month) will also be calculated:

- Baseline to Week 12
- Week 12 to Week 24
- Week 24 to Week 36
- Week 36 to Week 48

And

- Baseline to Week 24
- Week 24 to Week 48

... and so forth when reporting the extension phase data

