5.2.4 Time to stand

The time to stand is recorded as part of the NSAA. If the subject is unable to perform the NSAA the reason will be recorded. If the time to stand is missing and the response to rise from floor activity with the NSAA is "unable" then the time to stand will be considered informative missing and taken as the worst time recorded (over all subjects and assessments). Otherwise, if the reason given for not performing the assessment is related to the subject's medical condition (i.e. informative) the time to stand will be taken as the worst time recorded, otherwise it will be taken as missing.

Changes from baseline will be calculated.

The following velocities of change (change per month) will also be calculated:

- Baseline to Week 12
- Week 12 to Week 24
- Week 24 to Week 36
- Week 36 to Week 48

And

- Baseline to Week 24
- Week 24 to Week 48

... and so forth when reporting the extension phase data

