9.6.3 North Star Ambulatory Assessment

Scores and changes from baseline will be summarized by visit using descriptive statistics for both the total score and the linearized score.

The individual activity scores will be summarized by visit using a shift table from baseline. Marginal totals will be included.

The number (percentage) of subjects who have lost 0, 1, 2...activities will be tabulated by visit.

The velocities of change for the total score will be summarized using descriptive statistics. Velocities of change will also be analyzed using the methods described in [Section 9.6.1](#).

The 6MWD and NSAA total score changes from baseline will be plotted together against visit in trellis plots with one subject per plot. The two parameters will have different y-axes and a legend will be provided to distinguish 6MWD and NSAA lines on the plot.

Individual subject total scores will be plotted against age as individual line plots (spaghetti plots).

Week 12, 24, 36 and 48 changes from baseline for the total scores will also be plotted against age on Day 1 and baseline, using different symbols to identify the Week. The Pearson correlation coefficient (for each week) will be footnoted on the plots.

The box and whisker and mean change from baseline plots will only be presented for the total scores.

The number and percentage of subjects who lose ambulation will be summarized by visit.

9.6.4 10-Metre Run/Walk

Scores and changes from baseline will be summarized by visit using descriptive statistics.

The velocities of change will be summarized using descriptive statistics. Velocities of change will also be analyzed using the methods described in [Section 9.6.1](#).

Individual subject data will be plotted against age as individual line plots (spaghetti plots).

Week 12, 24, 36 and Week 48 changes from baseline will also be plotted against age on Day 1 and baseline, using different symbols to identify the Week. The Pearson correlation coefficient (for each week) will be footnoted on the plots.

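### A 10-metre test that a boy starts but is physically unable to finish is scored only on his speed before stopping, so the failure can appear as no change or as an improvement

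*SAP*

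**What the plan says.** SAP 5.2 sets the trigger: "A reason of 'Subject physically unable' will be regarded as informative, whilst 'Site staff/facility unavailable' is not informative". For informative failures of the 10-metre run/walk, SAP 5.2.3 gives two outcomes: "the time will be taken as the worst score recorded (over all subjects and assessments) whilst on treatment or the derived time adjusted for the" metres covered. The sentence pairs them in order. A test not performed takes the worst score, and a test not completed takes the derived time. The formula is "The derived time adjusted for the distance = (10/distance in metres) x time recorded".

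The data that feed it are set out just before: "For an assessment not completed the distance and duration of time walked will also be recorded". The section gives no minimum distance, no floor and no failure category for a test that was started. If a repeat test is done, the shortest completed time is used.

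The value then goes into the analysis. SAP 9.6.4 states "Scores and changes from baseline will be summarized by visit using descriptive statistics", and the same section has velocities estimated by the mixed model of SAP 9.6.1. SAP 9.10 plots the change against exposure, MRS, biopsy and other functional measures, with Pearson correlations.

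The SAP treats medical inability differently on its other performance tests:
- Time to stand, when the boy is unable to rise: "the time to stand will be considered informative missing and taken as the worst time recorded (over all subjects and assessments" (SAP 5.2.4).
- Six-minute walk not performed or not completed: "the 6MWD will be taken as zero or the recorded 6MWD respectively" (SAP 5.2.1).
- NSAA and PUL not performed: zero (SAP 5.2.2 and 5.2.6).

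**The concern.** Proration assumes that the boy would have covered the remaining metres at the speed he had kept up so far. For a boy who stopped because he was physically unable to go on, that is the assumption the event contradicts. The rule also puts a break between two neighbouring states. A boy who cannot start gets the slowest time in the study, while a boy who manages a few metres at his usual pace is scored as unchanged.

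At stake are the by-visit mean changes, the velocities and the correlations for this endpoint. The study has no concurrent control group in which the same rule would operate, and protocol 12.1.4 allows changes from baseline to be compared with historical data. Some boys who lost the ability to finish 10 m could be counted there as stable or improved.

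**Working it through.** The plan gives no numerical result for this rule, so there is no figure to reproduce.

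**Inputs from the documents**
- Formula and recorded items (distance, and time spent walking): SAP 5.2.3.
- Definition of change: "Change from baseline is defined as (value at post-baseline visit – value at baseline" (SAP 5.1). On a timed test a negative change is an improvement.
- Cohorts 1 and 2, tabulated together: about 30 + about 10 = about 40 boys (SAP 3.1 and 9.6.1).

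**Assumptions, because the documents give no times:** baseline 6.0 s, worst on-treatment time 20 s, and +0.5 s for boys who finish.

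**Step 1: what the formula measures.** Let d be the distance covered, t the time walked and v = d/t. The derived time is (10/d) x t = 10/v. The change from baseline is 10/v - 10/v_B, where v_B is the baseline speed. For a given speed the distance cancels: stopping at 2, 5 or 8 m scores the same as finishing at that speed. The change is zero if v = v_B, negative if v > v_B and positive if v < v_B.

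**Step 2: examples at a 6.0 s baseline**

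| Stops at | Time walked | Derived time | Change |
|---|---|---|---|
| 5 m | 3.0 s | (10/5) x 3.0 = 6.0 s | 0.0 s |
| 8 m | 4.4 s | (10/8) x 4.4 = 5.5 s | -0.5 s |
| 4 m | 2.0 s | (10/4) x 2.0 = 5.0 s | -1.0 s |
| 2 m | 1.0 s | (10/2) x 1.0 = 5.0 s | -1.0 s |
| 5 m | 4.5 s | (10/5) x 4.5 = 9.0 s | +3.0 s |
| 1 m | 3.0 s | (10/1) x 3.0 = 30.0 s | +24.0 s |

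A boy with the same baseline who finishes in 6.5 s scores +0.5 s. He is ranked below each of the first four boys, who did not finish. The last row passes the assumed 20 s worst time, so the rule can also err in the other direction.

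**Step 3: other baselines.** For baselines from 5 to 10 s, the same speed before stopping always gives 0. A speed 20% faster gives -0.83 to -1.67 s, and 20% slower gives +1.25 to +2.50 s, whatever distance was reached.

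**Step 4: illustrative effect on a mean of 40.** Let k boys fail after walking 20% faster than at baseline. Each scores -1.0 s under the present rule, or 20 - 6 = +14.0 s if given the worst time. Mean change = [(40 - k) x 0.5 + k x c]/40, with c = -1.0 or +14.0.

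| k | Present rule | Worst time |
|---|---|---|
| 1 | (19.5 - 1)/40 = +0.46 s | (19.5 + 14)/40 = +0.84 s |
| 2 | (19 - 2)/40 = +0.43 s | (19 + 28)/40 = +1.18 s |
| 4 | (18 - 4)/40 = +0.35 s | (18 + 56)/40 = +1.85 s |

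Each such boy shifts the mean by 15/40 = 0.375 s between the two rules. Under the present rule the mean falls, which looks better, as more boys fail. That direction depends on the assumed faster speed before stopping. The last column depends on the assumed 20 s.

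**The case against.** A reader might infer that the endpoint cannot register loss of the ability to complete 10 m, or that the rule always pulls mean change towards no decline. The documents support neither. The formula uses measured speed, so a boy who slows before stopping scores worse (rows five and six of the first table), and complete inability takes the worst time. A boy who is about to fail may well slow first. Protocol 6.5.2 has boys start from just behind the line, so a short part-walk may include acceleration and understate his speed; this last step is inference.

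Other points count in the rule's favour:
- Some derivation is needed, because no 10 m time exists and the raw partial time would flatter even more. The six-minute walk comparison is therefore imperfect: there, distance is itself the outcome. Still, the SAP also records the time walked in that test and chooses not to prorate.
- Non-completion may be uncommon in the main analysis. Boys in Cohorts 1 and 2 had to walk at least 300 m unassisted at screening, and the 10 m may be walked. Cohort 3 is summarised separately.
- Loss of ambulation and lost NSAA activities are reported on their own, and SAP 9.1 and 9.6.1 tabulate the number of imputed values.
- The worst observed time is an extreme value that depends on the data.

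These points limit the consequence and argue for a sensitivity analysis. They do not repair the rule. The imputed count discloses the values but leaves them in the means, and nothing in 5.2.3 stops a failed test from scoring as an improvement.

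**Conclusion.** The point holds in a limited form. For a test started but not completed for an informative reason, and with no completed repeat, the score depends only on speed before stopping. No change or an improvement follows whenever that speed was held or exceeded; this is algebra and needs no assumed times. It is out of line with the SAP's treatment of inability on time to stand, NSAA, PUL and a 10-metre test not performed.

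The size of the effect is unknown. The documents give neither the frequency of non-completion nor any speeds before stopping, and the figures in seconds are illustrations. The timed tests are exploratory endpoints in an open-label study not sized on power, and no decision rule rests on them. The change is still worth making because it is small, and the open-ended extension phase gives more opportunity for such failures.

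**What to change.** In SAP 5.2.3, score informative non-completion in the same way as informative non-performance: the worst completed on-treatment time over all subjects and assessments, or the prorated time if that is longer. Report the prorated time in listings and repeat the summaries with it as a sensitivity analysis. State that the worst time is taken from completed tests, since the present text does not say whether derived times count towards it. No new count of imputed values is needed.

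The change costs one or two sentences and one additional set of tables. It has two downsides. A near-finish, such as stopping at 9 m, is scored as a failure. One extreme value can also move a mean of about 40 boys: in the illustration, a failing boy given 20 s instead of a prorated 5.0 s moves it by 0.375 s. The sensitivity analysis would show both effects. The clause for a longer prorated time keeps a very slow part-walk (30.0 s in the example) from being improved to 20 s. It leaves that boy beyond one who could not start, which can already happen under the present rule if the worst score means completed times only.

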5.2.4 Time to stand

The time to stand is recorded as part of the NSAA. If the subject is unable to perform the NSAA the reason will be recorded. If the time to stand is missing and the response to rise from floor activity with the NSAA is "unable" then the time to stand will be considered informative missing and taken as the worst time recorded (over all subjects and assessments). Otherwise, if the reason given for not performing the assessment is related to the subject's medical condition (i.e. informative) the time to stand will be taken as the worst time recorded, otherwise it will be taken as missing.

Changes from baseline will be calculated.

The following velocities of change (change per month) will also be calculated:

- Baseline to Week 12
- Week 12 to Week 24
- Week 24 to Week 36
- Week 36 to Week 48

And

- Baseline to Week 24
- Week 24 to Week 48

... and so forth when reporting the extension phase data

5.2.5 Paediatric Outcomes Data Collection Instrument (PODCI)

The PODCI will be completed by the parent/carer. It consists of 86 questions from which five scales and one global scale are calculated (see [Appendix 3](#)). The five scales are:

- 1) Upper extremity and physical function core scales;
- 2) Transfer and basic mobility core scale,
- 3) Sports and physical functioning core scale,
- 4) Pain/comfort core scale and
- 5) Happiness core scale.

For each scale the mean score (referred to as the “mean of items”) will be calculated. If a question contained within a scale is not answered, that question is not included in the calculation of the mean score. For each scale there is a minimum number of questions that have to be answered, otherwise the score is considered missing.

The scale’s mean score is standardized into a score ranging between 0-100, where a higher score indicates fewer limitations due to DMD. The Standardized Score will be used in analyses.

The global functioning scale is calculated by taking the mean of the “standardized scores” from the following scales:

- 1) Upper extremity and physical function,
- 2) Transfer and basic mobility,
- 3) Sports and physical functioning and
- 4) Pain/comfort.

The scoring algorithms can be found in [Appendix 4](#).

No imputation will be used for missing PODCI scores.

Changes from baseline will be calculated for each scale standardized score and the global functioning scale score.

5.2.6 Performance of the Upper Limbs

The PUL assessment (Version 2) was specifically designed to assess upper limbs in patients with DMD. It includes 22 items subdivided into high level shoulder (6 items), middle level elbow (9 items) and distal level wrist and hand (7 items) dimensions to test shoulder, elbow, and distal upper limb performance reflecting functional tasks (see [Appendix 4](#)). Prior to assessing these 22 items an entry level score (entry item) is determined. For weaker subjects, a low score on the entry item means high level items do not need to be performed with the shoulder dimension. Each item is scored on a 0-2 scale, except Items 15 and 22 which are scored as either 0 or 1. For all items a higher score indicates better performance. Each dimension will be scored separately with a maximum score of 12 for the shoulder level, 17 for the elbow level, and 13 for the distal level. A total score can be achieved by adding the three level scores (max global score 42).

If the subject is unable to perform the assessment the reason will be recorded. If the reason given is related to the subject’s medical condition (i.e. informative) the score will be taken as 0, otherwise the score will be taken as missing.

Changes from baseline will be calculated for each dimension and the total score.

5.3 Pharmacodynamic Assessments

5.3.1 Leg MRI/MRS (Cohorts 1 and 2)

The following leg muscle MRI/MRS parameters will be measured at Baseline and Weeks 12, 24, 36 and 48 during the first 48 weeks and then 6 monthly during the extension phase:

- MRS method
 - Fat Fraction in the Vastus Lateralis (MRS_FF_VL)
 - Fat Fraction in the Soleus (MRS_FF_SOL)

- Water Transverse Relaxation Time (1H2O-T2) in the Vastus Lateralis (MRS _T2_VL)
- Water Transverse Relaxation Time (1H2O-T2) in the Soleus (MRS _T2_SOL)
- 8 point Dixon method
 - Fat Fraction in the Vastus Lateralis (DIX_FF_VL)
 - Fat Fraction in the Soleus (DIX_FF_SOL)
 - Fat Fraction in the Biceps Femoris (DIX_FF_BFLH)
- MRI method
 - Proton Transverse Relaxation Time (T2) in the Vastus Lateralis (MRI_T2_VL)
 - Proton Transverse Relaxation Time (T2) in the Soleus (MRI_T2_SOL)
 - Proton Transverse Relaxation Time (T2) in the Biceps Femoris (MRI_T2_BFLH)

The MRS parameters from the Vastus Lateralis and Soleus are considered the primary MRI/MRS parameters for the study.

The fat fractions are reported as percentages, whilst T2 parameters are reported in ms.

Imputation will not be used for any missing data.

If a subject withdraws from the study prematurely they will also be assessed at the termination visit if not performed in the last 6 weeks.

Changes from baseline will be calculated.

The following velocities of change (change per month) will also be calculated for the MRS fat fraction measurements:

- Baseline to Week 12
- Week 12 to Week 24
- Week 24 to Week 36
- Week 36 to Week 48

And

- Baseline to Week 24
- Week 24 to Week 48

... and so forth when reporting the extension phase data

